APPENDIX K. CORTICOSTEROID CONVERSION TABLE

Corticosteroid Conversion Table	
Glucocorticoid	Approximate Equivalent Dose (mg)
Short-Acting	
Cortisone	25
Hydrocortisone	20
Intermediate-Acting	
Methylprednisolone	4
Prednisolone	5
Prednisone	5
Triamcinolone	4
Long-Acting	
Betamethasone	0.6 - 0.75
Dexamethasone	0.75

References:

Dixon JS. Second-line Agents in the Treatment of Rheumatic Diseases. Informa Health Care. 1991;456.

APPENDIX M. PROTOCOL AMENDMENT SUMMARY OF CHANGES

Previous Protocol Versions

Protocol	Date
Version 1.0	02 February 2018
Version 2.0	11 June 2018
Version 3.0	15 March 2019
Version 4.0	02 October 2019

The purpose of this amendment is to correct minor clerical errors for consistency and other administrative changes throughout the protocol in addition to the following:

- Rationale:** To update pneumococcal and influenza vaccination requirements in Section 5.4.
 - Updated pneumococcal influenza vaccination requirements to remove requirement for re-vaccination if subjects were already vaccinated.
- Rationale:** To update the list of signatories in Appendix C per current standard operating procedure.
 - Replaced [REDACTED] and [REDACTED] with [REDACTED].
 - Removed [REDACTED] as a signatory.
- Rationale:** To delete the progression-free survival follow-up visits.
 - Removed progression-free survival follow-up visits to the Schedule of Activities, Appendix D.
 - Removed the subject criteria for progression-free survival follow-up and the frequency of the visits in Appendix E.
- Rationale:** To delete the survival follow-up assessments.
 - Removed survival follow-up visits to the Schedule of Activities, Appendix D.
 - Removed the survival status activity row to the Schedule of Activities, Appendix D.
 - Removed the summary of the data collected and the frequency for the survival follow-up visits in Appendix E.

### 3.0 Introduction

This statistical analysis plan (SAP) serves as a guide for the analysis of the efficacy and safety endpoints pertaining to ABT-199 Study M16-085.

Unless noted otherwise, all analyses will be performed using SAS version 9.4 or higher (SAS Institute Inc., Cary, NC 27513) in the UNIX operating system.

This SAP will not be updated unless a proposed protocol amendment is expected to impact the data analysis.

### 4.0 Study Background

#### 4.1 Objective

The objective of this study is to determine the safety profile, tolerability, preliminary efficacy, recommended Phase 2 dose, and pharmacokinetics (PK) of venetoclax and pomalidomide combination therapy with dexamethasone (ven/pom/dex) in subjects with relapsed or refractory (R/R) multiple myeloma (MM) who have received  $\geq 3$  prior lines of therapy, including a proteasome inhibitor (PI) and an immunomodulatory drug (IMiD), or who are double-refractory to a PI and an IMiD.

#### 4.2 Study Design and Design Diagram

[figure not shown]
This is an open-label, multicenter study with two phases, diagrammed in [Figure 1](#).

1. **Dose escalation** will consider 6 – 12 subjects confirmed to be t(11;14)+ by an analytically-validated FISH assay per central laboratory testing before enrollment. Dose escalation will be guided by a Bayesian optimal interval (BOIN) design, based on the cumulative number of subjects who experience a DLT at the current combination dose. The subjects will be enrolled in cohorts of at least 3 subjects. The first cohort will be administered a 400 mg dose of venetoclax orally, once daily (QD). If acceptable safety and tolerability are observed at the completion of Cycle 1 in at least 3 DLT-evaluable subjects, the dose of venetoclax will be

escalated to 800 mg QD (the target dose). All subjects will be administered the approved dose of pomalidomide (oral 4 mg QD) and dexamethasone (40 mg once weekly (qw)). To be considered DLT-evaluable, subjects must complete at least 80% of pomalidomide and venetoclax dosing (or experience a DLT) during Cycle 1. DLTs are defined in the operations manual. Additional information regarding the BOIN design is provided in [Appendix A](#).

2. **Dose expansion** will consist of 2 independent arms. Arm A will consider t(11;14)+ subjects, and Arm B will consider non-t(11;14) subjects. All subjects who participate in this phase must be screened for t(11;14) translocation status before enrollment. Arm A will feature around 23 subjects and Arm B will feature around 27 subjects. All subjects will receive the ven/pom/dex combination until documented PD, unacceptable toxicity, withdrawal of consent, or they meet another criteria for discontinuation (see study protocol). Subjects may discontinue pomalidomide but continue receiving venetoclax QD for up to 2 years following the date of the last subject enrolled, provided they completed Cycle 1 of ven/pom/dex, continue to tolerate venetoclax, do not exhibit PD, and do not meet any criteria for discontinuation. AbbVie will work with the investigator to evaluate options for continued venetoclax therapy for subjects that continue to derive benefit after 2 years of treatment.

**Figure 1. Study Design Diagram**

## 4.3 Endpoints

### 4.3.1 Primary Efficacy Endpoint

The primary efficacy endpoint is the overall response rate (ORR), which is defined as the proportion of subjects experiencing a stringent complete response (sCR), complete response (CR), very good partial response (VGPR), or partial response (PR).

### 4.3.2 Secondary Efficacy Endpoint

Key secondary efficacy endpoints include progression-free survival (PFS), duration of response (DOR), and time to progression (TTP). PFS for a given subject is defined as the number of days from the date of first dose until the date of the first documented PD or death due to any cause, whichever occurs first. All events of PD will be included, regardless of whether the event occurred while the subject was still taking study drug or had previously discontinued study drug. If the subject does not experience PD or death, the subject's data will be censored. See [Table 1](#) for details.

**Table 1. Event and Censoring Dates Used in PFS**

Situation	Option for End-Date	Outcome
No baseline assessment	Date of first dose	Censor
PD or death at scheduled assessment date or before the next scheduled assessment	Date of PD or death (whichever occurs first)	Event
PD or death after exactly one missing assessment	Date of PD or death (whichever occurs first)	Event
PD or death after two or more missing assessments	Date of first dose (if no adequate assessment is available prior to PD/death) or date of the last adequate assessment prior to PD/death	Censor
No PD and no death	Date of first dose (if no adequate assessment is available) or date of last adequate assessment	Censor

Time to Disease Progression (TTP) for a given subject is defined as the number of days from the date of first dose to the date of first documented PD or death due to MM,

whichever occurs first. If the subject does not have an event of PD and the subject has not died due to MM, the subject's data will be censored. See [Table 2](#) for details.

**Table 2. Event and Censoring Date Used in TTP**

Situation	Option for End-Date	Outcome
No baseline assessment	Date of first dose	Censor
PD or death due to multiple myeloma at scheduled assessment date or before the next scheduled assessment	Date of PD or death (whichever occurs first)	Event
PD or death due to multiple myeloma after exactly one missing assessment	Date of PD or death (whichever occurs first)	Event
PD or death due to multiple myeloma after two or more missing assessments	Date of first dose (if no adequate assessment is available prior to PD/death) or date of the last adequate assessment prior to PD/death	Censor
No PD and no death due to multiple myeloma	Date of first dose (if no adequate assessment is available) or date of last adequate assessment	Censor

Duration of Response (DOR) for a given subject is defined as the number of days from the date of that subject's first documented response (PR or better) to the date of first documented PD or death due to multiple myeloma, whichever occurs first. If the subject with a documented response does not have an event of PD and the subject has not died due to MM, the subject's data will be censored. See [Table 3](#) for details. Subjects who never achieve a documented response will not be included in the analysis of DOR.

**Table 3. Event and Censoring Date Used in DOR**

Situation	Option for End-Date	Outcome
No baseline assessment	Date of first dose	Censor
PD or death due to multiple myeloma at scheduled assessment date or before the next scheduled assessment	Date of PD or death (whichever occurs first)	Event
PD or death due to multiple myeloma after exactly one missing assessment	Date of PD or death (whichever occurs first)	Event
PD or death due to multiple myeloma after two or more missing assessments	Date of the last adequate assessment prior to PD/death	Censor
No PD and no death due to multiple myeloma	Date of the last adequate assessment	Censor

### 4.3.3 Safety Endpoint

Safety evaluations include adverse event (AE) monitoring, physical examinations, vital sign measurements, electrocardiogram (ECG) variables, and clinical laboratory testing (hematology, chemistry, and urinalysis) as a measure of safety and tolerability for the entire study duration.

### 4.3.4 Pharmacokinetic Endpoints

PK samples will be collected and analyzed for venetoclax and pomalidomide concentrations. The maximum observed plasma concentration ( $C_{max}$ ), time to  $C_{max}$  ( $T_{max}$ ), and the area under the plasma concentration vs time curve (AUC) will be determined using noncompartmental methods.

### 4.3.5 Biomarker Research Endpoints

Biospecimens (blood, serum, plasma, bone marrow aspirate, and bone marrow core biopsy tissue) will be collected at specified time points throughout the study to evaluate known or novel disease-related or drug-related biomarkers. Types of biomarkers analyzed may include nucleic acids, proteins, lipids, or metabolites. Some biomarkers of

potential interest can be found in Section 3.2 of this SAP, and any noteworthy results may be included in the clinical study report. Details pertaining to biomarker research endpoints can be found in the operations manual.

#### 4.4 Sample Size Justification

Approximately 60 subjects will be enrolled into this two-part study. Dose escalation will enroll around 10 subjects, and dose expansion will enroll around 50 subjects.

1. **Dose Escalation** will enroll at least 3 subjects per cohort according to a BOIN design, for a total of 6 – 12 subjects.
2. **Dose Expansion** will enroll around 23 subjects in Arm A, and 27 subjects in Arm B.
  - a. Arm A: t(11;14)+: The historical ORR for pom/dex is 35%. By adding venetoclax to this combination, an ORR of 70% is clinically meaningful for t(11;14)+ subjects. Allowing for a maximum one-sided type 1 error rate of 0.025, and assuming an ORR of 35% from the historical data, 23 subjects will provide 90% power if the true ORR for t(11;14)+ subjects treated with ven/pom/dex is 70%.
  - b. Arm B: Non-t(11;14): The historical ORR for pom/dex is 35%. By adding venetoclax to this combination, an ORR of 60% is clinically meaningful for non-t(11;14) subjects. The sample size for Arm B will be approximately 27 subjects. Allowing for a maximum one-sided type 1 error rate of 0.1, and assuming an ORR of 35% from the historical data, 27 subjects will provide 90% power if the true ORR for non-t(11;14) subjects treated with ven/pom/dex is 60%.

## 4.5 Interim Analysis

During the dose escalation phase, review meetings will be conducted at the completion of Cycle 1 in at least 3 evaluable subjects per cohort.

[figure not shown]
Since this is an open-label study, both arms of the dose-expansion phase will be continuously monitored. Interim analysis (IA) may be conducted when adequate data from approximately 10 and 16 subjects are available from Arms A and B, respectively. Figure 2 displays some guidelines for go/no-go decisions for the IA, broken down by arm. Observed ORRs in the green region may be used as evidence to accelerate studies of venetoclax in combination with IMiDs to earlier lines of therapy. Results in the yellow region suggest evaluating the depth and duration of response for more guidance.

**Arm A:** the probability of making the wrong "go" decision is 2.6%, given a true ORR of 35%, and the probability of making the wrong "no-go" decision is 1.1%, given a true ORR of 70%. The final analysis for Arm A will include the subjects from the escalation portion of the study, resulting in a grand total of around 29 t(11;14)+ subjects.

**Arm B:** the probability of making the wrong "go" decision is 2.3%, given a true ORR of 35%, and the probability of making the wrong "no-go" decision is 1.9%, given a true ORR of 60%.

The final go/no-go decision will be based on totality of efficacy and safety data.

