Subjects must complete at least 80% of pomalidomide dosing and at least 80% of venetoclax dosing in Cycle 1 or experience a DLT to be considered evaluable for dose-escalation decisions. Subjects not DLT-evaluable may be replaced as necessary to meet minimum requirement for dose escalation. DLTs are defined in Section 6.5.

Additional information regarding the BOIN design will be provided in the SAP.

During Part 1, dose review meetings will be conducted at the completion of Cycle 1 in at least 3 evaluable subjects in each cohort.

All subjects who participate in the dose-escalation phase of the study will undergo bone marrow aspirate collection for cytogenetic determination at baseline.

Part 2: Dose Expansion

[figure not shown]
The dose-expansion phase of the study will consist of 2 arms. Arm A will further evaluate the safety and efficacy profile of the combination therapy with venetoclax, pomalidomide, and dexamethasone in approximately 23 subjects positive for t(11;14) translocation. Arm B will further evaluate the safety and

efficacy profile of the combination therapy with venetoclax, pomalidomide, and dexamethasone in approximately 27 subjects negative for t(11;14) translocation. Subjects will receive the venetoclax dose that is determined to be safe in Part 1 + pomalidomide (4 mg PO, QD) + dexamethasone (40 mg qw). All subjects who participate in the dose-expansion phase of the study are required to undergo bone marrow aspirate collection at screening for determination of t(11;14) status before enrollment.

See Section 5.1 for information regarding eligibility criteria.

Review of the efficacy and safety data will be completed on an ongoing basis. During Part 1, dose review meetings will be conducted at the completion of Cycle 1 with at least 3 evaluable subjects in each cohort. Additional reviews will be held as deemed necessary based on study events or data.

Figure 1. Study Design

Dex = dexamethasone; Pom = pomalidomide; QD = once daily; qw = once weekly; Ven = venetoclax

Note: Venetoclax will be administered once daily from Day 1 through Day 28 of each cycle. Pomalidomide will be administered once daily from Day 1 through Day 21 of each cycle.

Hematology must be completed before the initiation of each subsequent cycle of combination therapy. Subjects must meet the following minimum criteria to continue combination therapy:

- absolute neutrophil count (ANC) $\geq 500/\mu\text{L}$; growth factor support is allowed after Cycle 1

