 - serum free-light chain (FLC) ≥ 10 mg/dL provided serum FLC ratio is abnormal
- ✓ 8. Has received at least 1 prior line of therapy.
 - A line of therapy consists of > 1 complete cycle of a single agent, a regimen consisting of a combination of several drugs, or a planned sequential therapy of various regimens
- ✓ 9. Must meet all of the following prior antimyeloma treatment parameters:
 - subject must have received at least 2 consecutive cycles of lenalidomide or a lenalidomide-containing regimen
 - subject must be refractory to lenalidomide
 - subject must have documented evidence of PD based on the investigator's determination of response as defined by the modified IMWG criteria on or after the last regimen
 - subject who received only 1 line of prior treatment must have demonstrated PD on or within 60 days of completion of the lenalidomide-containing regimen
 - subject must have been exposed to a PI alone or in combination with another agent
 - subject must have had a response of PR or better to prior therapy based on the investigator's determination of response as defined by IMWG criteria
- ✓ 10. Has t(11;14) status determined by an analytically validated fluorescent in situ hybridization (FISH) assay per central laboratory testing of a bone marrow aspirate sample and meets the following criteria:
 - For Part 1: MM subjects independent of cytogenetic profile
 - For Part 2, Arm A: subject must be t(11;14) positive
 - For Part 2, Arm B: subject must be t(11;14) negative
- ✓ 11. An Eastern Cooperative Oncology Group (ECOG) performance status ≤ 2 .

Subject History

- ✓ 12. No history of clinically significant medical conditions within the last 6 months that, in the investigator's opinion, would adversely affect the subject's participation in the study.

- ✓ 13. No history of **any active malignancies**, including myelodysplastic syndromes, within the past 3 years except for the following:

 - adequately treated in situ carcinoma of the cervix uteri or the breast;
 - basal cell carcinoma of the skin or localized squamous cell carcinoma of the skin;
 - prostate cancer Gleason Grade 6 or lower AND with stable prostate-specific antigen levels off treatment; or
 - previous malignancy with no current evidence of disease, and which was confined and surgically resected (or treated with other modalities) with curative intent and unlikely to impact survival during the duration of the study.
- ✓ 14. None of the following conditions:

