7.2 Determination of Sample Size

Approximately 60 subjects will be enrolled into this 2-part study.

Part 1, Dose Escalation

Part 1 will enroll approximately 3 to 6 subjects per cohort using a BOIN design, resulting in a total of 6 to 12 subjects.

Part 2, Dose Expansion

Part 2 will enroll approximately 50 subjects.

Arm A: t(11;14)-Positive

The historical ORR for pomalidomide + dexamethasone is 35%.^{13,14} By adding venetoclax to this combination, an ORR of 70% is clinically meaningful for t(11;14)-positive subjects. The sample size for Arm A will be approximately 23 subjects. Allowing for a maximum 1-sided type 1 error rate of 0.025 and assuming an ORR of 35% from the historical data, 23 subjects will provide 90% power if the true ORR for t(11;14)-positive subjects treated with venetoclax + pomalidomide + dexamethasone is 70%.

Arm B: t(11;14)-Negative

The historical ORR for pomalidomide + dexamethasone is 35%. By adding venetoclax to this combination, an ORR of 60% is clinically meaningful for t(11;14)-negative subjects. The sample size for Arm B will be approximately 27 subjects. Allowing for a maximum 1-sided type 1 error rate of 0.1 and assuming an ORR of 35% from the historical data, 27 subjects will provide 90% power if the true ORR for t(11;14)-negative subjects treated with venetoclax + pomalidomide + dexamethasone is 60%.

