7.3 Definition for Analysis Populations

The Full Analysis Set (FAS) includes all subjects who received at least 1 dose of study drug. The FAS will be used for all safety, PK, efficacy and baseline analyses.

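### The SAP adds the escalation subjects to the Arm A final analysis, but the current protocol enrols Part 1 regardless of t(11;14) status and sizes Arm A at about 23, so the Arm A primary set is not fixed

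*SAP*

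**What the plan says.** **SAP (version 1.0, 06 Feb 2018).** Section 4.2 describes escalation as "6 – 12 subjects confirmed to be t(11;14)+ by an analytically-validated FISH assay" and defines the expansion arms: "Arm A will consider t(11;14)+ subjects, and Arm B will consider non-t(11;14) subjects". Sections 4.2 and 4.4 put Arm A at around 23. Section 4.5 then says of the final analysis: "Arm A will include the subjects from the escalation portion of the study, resulting in a grand total of around 29 t(11;14)+ subjects". Section 6.1 gives the exact binomial test for Arms A and B, at 0.025 and 0.1, without saying which subjects make up Arm A. Section 3.0 provides for a SAP update only when a protocol amendment is expected to affect the analysis.

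**Protocol (24 June 2020).** Section 5.1, criterion 10, reads: "For Part 1: MM subjects independent of cytogenetic profile". Section 4.1 places the two arms in the dose-expansion phase, with Arm A evaluated "in approximately 23 subjects positive for t(11;14) translocation". Section 7.2 states "The sample size for Arm A will be approximately 23 subjects" and bases the 0.025 error rate and 90% power on that number. For escalation it says "Part 1 will enroll approximately 3 to 6 subjects per cohort using a BOIN design", 6 to 12 in all. Section 7.4 tests Arms A and B and does not mention Part 1. In section 7.3 the Full Analysis Set is every treated subject: "The FAS will be used for all safety, PK, efficacy and baseline analyses".

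**The concern.** The pooling sentence made sense when every escalation subject had to be t(11;14)-positive. The protocol no longer requires that. Adding all escalation subjects would now contradict the sentence's own t(11;14)+ label. Adding only some needs a selection rule, and the sentence gives none. It also does not say whether the 400 mg cohort counts if Part 2 runs at another venetoclax dose.

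The FAS does not settle the matter, because it covers both parts and assigns nobody to an arm. A programmer could defend either Part 2 Arm A alone or Arm A plus escalation subjects. The study is open-label and SAP 4.5 says both expansion arms are continuously monitored, so the choice could be made with the responses in view. It has to be settled before the final analysis.

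**Working it through.** **1. The plan's figure of 29.** Arm A is 23 (protocol 7.2, SAP 4.4). Adding the minimum escalation size gives 23 + 6 = 29, so the figure reproduces. The SAP's around 10 (section 4.4) gives 23 + 10 = 33, and the maximum of 12 gives 35. Under current eligibility the number of t(11;14)-positive Part 1 subjects can be anything from 0 to 12, so a positive-only pool runs from about 23 to 35.

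**2. The test on each set.** Inputs from protocol 7.2 and 7.4: null ORR 35%, alternative 70%, one-sided 0.025. The critical value r is the smallest integer with P(X ≥ r | n, 0.35) ≤ 0.025. Size is that probability, and power is P(X ≥ r | n, 0.70).

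| n | Set | Success at | Size | Power at 70% |
|---|---|---|---|---|
| 23 | Part 2 Arm A only | ≥ 14 | 1.0% | 88.0% |
| 26 | plus 3 | ≥ 15 | 1.5% | 94.0% |
| 29 | plus 6 | ≥ 16 | 2.1% | 97.1% |
| 33 | plus 10 | ≥ 18 | 1.7% | 98.0% |
| 35 | plus 12 | ≥ 19 | 1.5% | 98.4% |

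The power column assumes that every subject has a true ORR of 70%.

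**3. Same Arm A data, opposite conclusions.**
- P(X ≥ 13 | 23, 0.35) = 0.028, so 13/23 fails. Adding 3/6 gives 16/29, with P(X ≥ 16 | 29, 0.35) = 0.021, which succeeds.
- P(X ≥ 14 | 23, 0.35) = 0.010, so 14/23 succeeds. Adding 1/6 gives 15/29, with P(X ≥ 15 | 29, 0.35) = 0.048, which fails.

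**4. How often the tests disagree when all subjects share one true ORR p.** Take X ~ Bin(23, p) and, independently, Y ~ Bin(m, p) for the m added subjects. Sum the joint probability over outcomes where exactly one of X ≥ 14 and X + Y ≥ r holds, with r = 16 for m = 6 and r = 19 for m = 12.

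| True ORR | m | Only pooled succeeds | Only Arm A succeeds | Total |
|---|---|---|---|---|
| 70% | 6 | 9.2% | 0.1% | 9.3% |
| 70% | 12 | 10.5% | 0.1% | 10.7% |
| 60% | 6 | 21.7% | 0.8% | 22.5% |
| 60% | 12 | 26.3% | 1.2% | 27.5% |
| 35% | 6 | 1.3% | 0.2% | 1.5% |

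Totals were rounded after summing.

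**5. Added subjects who respond differently.** The documents give no Part 1 ORR and no expected t(11;14) split, so this step is an assumption. The two rates used are the plan's own: 60% is the Arm B target and 35% the historical rate. Arm A is at 70%, and all m added subjects are at q.

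| q | m = 6 | m = 10 | m = 12 |
|---|---|---|---|
| 60% | 95.0% | 95.4% | 95.5% |
| 35% | 86.1% | 78.6% | 74.6% |

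The entries are pooled power, against 88.0% for Arm A alone. At 60% pooling still gains power. At 35% it loses power, and more as more subjects are added.

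**The case against.** The strongest reply has four parts.

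- **Version lag.** The SAP is dated four days after protocol version 1.0 (02 February 2018), and a later SAP may exist. This stands as a limit: the file shows only version 1.0, so the conflict is established for these two documents and no further.
- **The texts can be reconciled.** Around 23 is the number enrolled in Arm A and around 29 the number analysed. Protocol 7.4 does not forbid pooling and leaves efficacy detail to the SAP, and the t(11;14)+ label suggests pooling positive subjects only. That is a sensible reading, and baseline status is determined for everyone (protocol 3.6). But it has to be inferred: the sentence takes in the escalation subjects without selection, and it is silent on the 400 mg cohort.
- **Little inferential harm.** Type I error holds under a common 35%, and most disagreement is extra power from a larger sample. Both statements are correct. The 60% row uses the Arm B target rather than Arm A's, and the worked examples sit next to the critical value. They show that the choice can matter, not that it usually will. The primary objective is safety, and go/no-go decisions rest on the totality of data, but the 0.025 test is still a stated analysis and needs a defined set.
- **A prespecified positive-only pool would serve equally well.** It would also remove the ambiguity, and with more power if those subjects share the Arm A rate. The essential step is to fix one set. Part 2 only is the default because the protocol sizes and tests Arm A that way.

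**Conclusion.** The problem is real and should be fixed. SAP 4.2 and 4.5 rest on a Part 1 population that the current protocol does not have. The pooling rule is therefore wrong as written, not merely short on detail, and SAP 6.1 does not repair it.

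The consequence is moderate. At the design ORR of 70%, shared by all subjects, the two candidate sets give opposite conclusions about one time in ten (9.3% with 6 added, 10.7% with 12). At 60% it is 22.5% to 27.5%. The size of the test is not threatened while all subjects share the null rate. Loss of power is a risk only if the added subjects respond much less well than Arm A, which is an assumption the documents cannot test. All figures take exactly 23 subjects in Arm A and independent responses.

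**What to change.** Before the Arm A final analysis:

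1. Bring the escalation population in SAP 4.2 into line with protocol 5.1.
2. State one primary Arm A set, in the same words, in SAP 4.5 and 6.1. Default: treated Part 2 Arm A subjects only, matching protocol 7.2 and 7.4, with success at 14 or more of 23.
3. Report as supportive the pool of these subjects with Part 1 subjects who are centrally confirmed t(11;14)-positive and were treated at the Part 2 dose level. Use the critical value for the resulting n, for example 15/26 or 16/29.
4. Delete the total of around 29, or restate it as a range.

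The change is to SAP wording only. No new data are needed, because t(11;14) status is already determined for all subjects. The price is fewer subjects in the headline Arm A estimate and the loss of any power gain from pooling: 88.0% at n = 23 against 97.1% at n = 29 if all 6 added subjects truly respond at 70%. A sponsor who prefers the positive-only pool as primary can choose it, provided the selection rule and the handling of the 400 mg cohort are written down before the final analysis.
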